6. STUDY PROCEDURES

Study participants will complete up to four, face to face interviews. The first interview is the screening interview where study eligibility is determined. Participants who meet the study eligibility criteria are enrolled in the study, randomized into one of the two study conditions. People who are randomly assigned to the experimental condition receive the study intervention and those who are randomly assigned to the control condition receive standard prison treatment and programming. All participants who are randomized to either study condition complete three additional follow up interviews: the baseline interview as well as 3- and 6-month interviews. Additionally, administrative data related to behavioral infractions and administrative segregation are collected at the 9-month time point.

6.a Description of Research Procedures

The study procedures are listed below.

All research interviews will take place in private locations in the prison:

First: Recruitment of study subjects will begin the month prior to the initiation of each intervention cycle. Correctional staff at the facility where the intervention is being delivered, will provide the research team with a list of all of the prisoners in their facility who meet the following criteria: a) 18 years and older: b) have mental health issues: c) have at least 1 year remaining on his or her prison sentence: d) do not have any restriction that would preclude the person from being in group gathering spaces within the prison; and e) do not have an intellectual or developmental disability.

Second: Research staff will go to the prison and invite potentially-eligible prisoners to meet with them in a private setting to learn about the study. During this initial meeting, research staff will provide participants with a flyer that describes the study and discuss potential participant's questions. The study flyer and discussions with potential participants will include information about the voluntary nature of the study and will explain that the person's decision about participation has no bearing on the person's criminal or civil cases. The research staff will also explain that the participant can end his or her participation in the study at any time during the recruitment or study process without negative consequences.

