Research staff will engage written Informed consent with all potential participants who express an interest in participation in the study during recruitment. Participants will also be asked to sign a HIPPA Authorization form allowing the study team to collect administrative pertaining to the study outcomes. Given concerns about the heightened risk of coercion that exists when conducting research in correctional settings, the research team took the following steps to minimize the risk of coercion in this study and obtain informed consent. First, although the recruitment process involved correctional staff, the involvement of these staff members was limited to helping the research team identify the pool of potential participants. Second, only the members of the research team approached potential participants to discuss

the study and obtain informed consent. Third, research staff conducted all informed consent meetings, and these meetings were held in private spaces. Fourth, correctional staff were instructed that study participation is strictly voluntary. Fifth, research staff did not communicate the outcomes of potential participant contacts with correctional staff. Taken together, these steps minimized the chance that correctional staff directly or inadvertently tried to influence individuals' decision to participate in the study. All researchers involved in recruitment were trained to cover consent information clearly and comprehensively. Furthermore, study flyers, consent forms, and HIPAA authorization forms were made available, in print form, to all potential participants.

6.c. Assessments and Data Collection

All study measures, with the exception of the receipt of Behavioral Infractions and Time Spent in Administrative Segregation, will be administered in face-to-face interviews using a paper-based interview. Receipt of Behavioral Infractions and Time Spent in Administrative Segregation are collected via administrative data. See appendix A for descriptions of study measures.

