9. STATISTICAL ANALYSIS

Given the preliminary nature of this study, statistical analyses of our outcomes will not be conclusive; rather we will examine the data for trends across time rather than relying exclusively on tests of statistical significance.

9.a. Primary Outcomes

The primary outcomes of this study are: Aggression, Receipt of Behavioral Infractions, and Time Spent in Administrative Segregation (see Appendix B).

9.b. Secondary Outcomes

The secondary outcomes of this study are those measures listed as Treatment Targets in the conceptual model: Interpersonal Problem Solving, Criminal Attitudes and Associates, and Levels of Impulsivity (see Appendix B).

9.c. Statistical Methods

Treatment Targets and Study Outcomes that are collected via a standardized measure (i.e. Social Problem Solving, Criminal Attitudes and Associates, Impulsivity, and Aggression) are collected at baseline as well as during follow-up periods (see Appendix A). Study Outcomes that are collected via administrative data (i.e. receipt of behavioral infractions and time spent in administrative segregation), however, are not collected as baseline, rather are summed cumulatively over the period extending from the 3-month follow-up period through the 9-month follow-up period.

To examine the impact of T4C-MI on study outcomes that are measured dichotomously and only collected during follow-up periods (i.e. receipt of disciplinary fractions and administrative segregation), we will use chi-square tests to examine between-group differences during the post-test period. To examine between-group post-test differences when these outcomes are measured as counts (i.e. number of behavioral infractions received and days spend in administrative segregation), nonparametric tests will be used to test differences in group medians (e.g. Mann-Whitney Test) and regressions that can accommodate count data (e.g. Poisson, negative binomial) will be employed.

For Treatment Targets and Study Outcomes that are measured continuously and collected at both baseline and follow-up periods (i.e. Social problem solving, impulsivity, criminal attitudes and associates, and aggression), we will use T-tests to examine between-group differences at posttest as well as mixed effects linear models where measurement occasion at level 1 is nested within the individual at level 2.

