The potential mediation effects of the proposed primary treatment targets on study outcomes will be explored using structural equation modelling (SEM) and generalized structural equation modelling (GSEM) frameworks to accommodate for variables that are measured both continuously and dichotomously.

9.d. Sample Size and Power

The sample will include up to 112 participants. Given the preliminary nature of this pilot study, our goals are not to fully test our hypotheses nor estimate effect sizes associated with T4C-MI. The main purpose of this R34 is to collect data on available sample size, sample attrition and sample retention and the generation of data and information necessary to conduct comprehensive power calculations for an R01. Nevertheless, here, the likelihood of detecting statistical significance will be increased due to the use of a longitudinal design with up to four measurements per subject on our treatment targets and outcome

measures. Also, our longitudinal design allows for each participant to serve as his/her own historic control, eliminating between-subjects variation and reducing standard errors, which increases power.

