11. PARTICIPANT RIGHTS AND CONFIDENTIALITY

11.a. Participant Confidentiality and Security

Project data and information will be maintained at the School of Social Work (SOSW) in the Tate-Turner-Kuralt Building on the campus of the University of North Carolina at Chapel Hill. At the SOSW, a secure, password-protected computer file for all project materials will be established with access restricted to the research team. All data schedules and interview forms will be filed securely away in locked file cabinets. All personal computers are password protected and servers are located on lockable offices.

Study subjects will be assigned unique, study identifiers. A separate master list of study IDs will be kept separately. Once data collection is complete, all personal identifiers will be destroyed. Once personal identifiers are destroyed all study subjects will be identified only by a unique study identifier.

All study documents will be maintained in locked filing cabinets within locked offices. Additionally, a Certificate of Confidentiality will be obtained to protect subject information. All interviews will take place in private settings within the prison. Participants will be informed that they can choose not to answer question(s) and can stop an interview at any time.

11.b. Study Discontinuation

There are four reasons that the study staff would withdraw a person from the research intervention and study: (1) in the unlikely event that a study participant would become aggressive or combative during the research intervention or research interview they would be withdrawn from the study; (2) if a subject's participation in the research intervention or interviews caused undue levels of emotional distress, either as reported by the subject or as observed by the researchers; and (3) if a subject asks to be withdrawn or declines further participation in the research intervention or follow-up research interviews at any point (4) if a subject is transferred or released from the prison where the experimental intervention is being delivered.

12. APPENDIX A: Assessment and Data Collection

	Initial Meeting and Screening Interview*	Baseline Interview	Delivery of the Study Intervention*	Three-month follow-up Interview	Six-month follow-up Interview	Nine-month administrative records check**
Screening and Intervention Delivery						
Recruitment and Informed Consent	X					
Participant Demographic and Background Characteristics	X					

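### Aggression and the treatment targets are seen only at interviews, and section 9.c analyses them without the prison records that could help correct for missed interviews linked to misconduct

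*Combined protocol and SAP*

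**What the plan says.** Section 6.c separates two data sources. For the scales: "All study measures, with the exception of the receipt of Behavioral Infractions and Time Spent in Administrative Segregation, will be administered in face-to-face interviews". For the other two primary outcomes: "Receipt of Behavioral Infractions and Time Spent in Administrative Segregation are collected via administrative data". Appendix A schedules aggression at baseline, 3 and 6 months, and the three treatment targets at baseline and 3 months only.

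For the scales, section 9.c says "we will use T-tests to examine between-group differences at posttest as well as mixed effects linear models", with occasions nested within person. It names no missing-data assumption, imputation, auxiliary variable or sensitivity analysis, and none appears elsewhere. The records are analysed separately, by chi-square, Mann-Whitney and count regression, after being "summed cumulatively over the period extending from the 3-month follow-up period through the 9-month follow-up period". The only joint modelling of targets and outcomes is the exploratory mediation work in section 9.c, which is not offered as a way to handle missing interviews.

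Loss to follow-up is expected. Section 9.d gives as a main purpose to "collect data on available sample size, sample attrition and sample retention". Section 11.b lists the reasons for withdrawal. One is that, should a participant "become aggressive or combative during the research intervention or research interview they would be withdrawn from the study". Another is transfer or release from the prison where the intervention is delivered.

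**The concern.** A person withdrawn for aggressive behaviour is unlikely to have the same aggression score as one who stays. The two arms are not equally exposed to that rule: behaviour in an interview can trigger it in either arm, but behaviour in the intervention can trigger it only in T4C-MI. If the more aggressive T4C-MI participants drop out of the interviewed sample more often than their control counterparts, that arm looks milder at follow-up even when the programme does nothing.

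The t-test takes the interviewed sample as it stands. The mixed model is better, because it borrows from a person's other scores on the same scale, but baseline aggression captures misconduct after baseline only in part. For the treatment targets, someone who misses the 3-month interview has at most a baseline score. Infractions and segregation need no interview and plausibly carry the missing information, yet the planned comparisons of these scales leave them out.

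**Working it through.** The plan states no alpha, power, effect size, SD or attrition rate, so there is no figure to reproduce. The only inputs from the documents are up to 112 participants (9.d) and equal allocation (3.a), hence 112/2 = 56 per arm. Everything else below is assumed for illustration.

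**Simulation 1: 6-month aggression.** SD 1 at each visit; correlation 0.5 between baseline and follow-up; a misconduct record M correlated 0.6 with mean follow-up aggression. The chance of missing both follow-up interviews is logit(p) = log(0.2/0.8) + s × M, where s = 0 is no link, 1 a link and 1.5 a strong link. There were 400,000 people per arm. Three estimates of the arm difference were compared:

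- t-test: difference in means among those interviewed
- own scores: regress the 6-month score on baseline within arm among those interviewed, then average the predictions over everyone randomised
- with records: the same, adding M to the regression

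| True effect | Link to misconduct | Missing, control / T4C-MI | t-test | Own scores | With records |
|---|---|---|---|---|---|
| 0 | same in both arms | 24% / 24% | 0.00 | 0.00 | 0.00 |
| 0 | steeper in T4C-MI (s = 0.5 v 1) | 21% / 24% | -0.06 | -0.04 | 0.00 |
| 0 | T4C-MI only | 20% / 24% | -0.107 | -0.075 | 0.00 |
| 0 | T4C-MI only, strong | 20% / 27% | -0.160 | -0.113 | 0.00 |
| -0.30 | same in both arms | 24% / 21% | -0.28 | -0.29 | -0.30 |
| -0.30 | T4C-MI only | 20% / 21% | -0.40 | -0.37 | -0.30 |
| -0.30 | control only | 24% / 20% | -0.20 | -0.23 | -0.30 |

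In the third row, own scores remove (0.107 - 0.075)/0.107 = 30% of the bias. A random-intercept mixed model of the kind in 9.c, fitted to 8,000 per arm, gave -0.07 in that scenario. Varying the correlation between record and aggression from 0.3 to 0.8, with the link in T4C-MI only and no effect, gave -0.05 to -0.14 for the t-test, -0.04 to -0.10 for own scores and 0.00 with records.

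**False positives.** In the third row, about 56 × 0.80 = 44.8 controls and 56 × 0.76 = 42.6 T4C-MI participants are interviewed, so SE = √(1/44.8 + 1/42.6) = 0.214 and bias/SE = 0.107/0.214 = 0.50. The two-sided 5% test then rejects with probability P(Z > 1.46) + P(Z < -2.46) = 0.079. Simulation at 56 per arm gave 7.9%; the strong link gave 11.3%, and the same link in both arms 4.8%.

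**Simulation 2: segregation as the driver.** Correlation 0.6 between baseline and follow-up aggression; 30% of controls ever segregated; correlation 0.3 to 0.5 between aggression and latent segregation risk; 10% of interviews missed by those never segregated. With no effect, segregated people miss 30% in control and 70% in T4C-MI. Overall missingness is 0.7 × 0.10 + 0.3 × 0.30 = 16% against 0.7 × 0.10 + 0.3 × 0.70 = 28%. The t-test bias is -0.06 to -0.11 SD, and own scores leave -0.02 to -0.07. With a true effect of -0.40 and 50 to 70% missed among the segregated in both arms, the t-test gives -0.37 to -0.35 with 42 to 38% power. Adding records gives -0.40 with 47 to 48% power.

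**Does the planned record window suffice?** Section 9.c sums records only from month 3. Take the no-effect case of simulation 2 for a 3-month outcome, let missingness follow segregation in months 0 to 3, and assume a latent correlation of 0.3 to 0.7 between the two periods. The t-test is biased by -0.06 to -0.10 SD; the baseline score alone leaves -0.04 to -0.07; adding records from months 3 to 9 leaves -0.02 to -0.06; adding records from months 0 to 3 leaves about zero.

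**The case against.** A reader might infer that segregated people cannot be interviewed, so that the aggression data are bound to be distorted. The documents do not say so. The restrictions in 4.b concern group gathering spaces, whereas interviews are private and planned for everyone. The only written link between misconduct and lost interviews is in 11.b, which itself calls the aggressive event unlikely. That stands: the mechanism is possible, its frequency is unknown, and the direction of any bias cannot be stated in advance.

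A reader might also infer that the trial already holds everything needed to correct the problem. It does not, as planned. The records are summed from month 3, so they miss the period before the only follow-up of the targets and the first follow-up of aggression. Nor does 11.b say whether records are still collected after withdrawal; if they stop, they are missing for the very people at issue.

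The size is modest. A bias of about 0.1 SD compares with a standard error of √(2/56) = 0.19 SD at full follow-up and about 0.21 with the assumed losses. The near-zero bias with records is a best case, because in the simulations missingness depends only on the record. Section 9 declares the analyses not conclusive, and 9.d disclaims full hypothesis testing and effect-size estimation.

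These points lower the stakes but do not remove the gap. Aggression remains a primary outcome, one withdrawal rule bears unequally on the arms, and the planned comparison omits plausibly predictive records from an extraction that is already scheduled.

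**Conclusion.** The concern holds in a limited form. Section 9.c analyses interview-only outcomes without the infraction and segregation records, and 11.b makes arm-dependent loss of aggressive participants possible. If that occurs, the assumed inputs give a t-test bias of about 0.05 to 0.15 SD (0.16 in the most extreme case run) and about 0.02 to 0.10 SD (at most 0.11) with the scale's own scores only. False positives for the t-test are roughly 6 to 11% instead of 5%. With equal missingness and no effect there is no bias; with equal missingness and a true effect the estimate shrinks by about 0.02 to 0.05 SD. Every rate and correlation is an assumption. The finding is that an inexpensive improvement is available, not that the aggression result is known to be wrong.

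**What to change.** In 9.c:

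- State the missing-data assumption. Analyse AQ-Short at 3 and 6 months and the 3-month targets for all randomised participants by multiple imputation, combined with Rubin's rules, or by an equivalent likelihood method.
- Include arm, facility, the scale's other scores, and infractions and segregation by interview window in the imputation model. The records are auxiliary variables only. They are post-randomisation outcomes and should not be covariates in the effect model.
- Keep the interviewed-only t-test as a secondary analysis, and report missed interviews by arm and record status.
- Add a simple sensitivity analysis, for example a delta shift applied to imputed scores.

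In 6 and 11.b:

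- Specify that the single extraction, where "administrative data related to behavioral infractions and administrative segregation are collected at the 9-month time point", includes dated events from randomisation. Reconcile the end of the window, which 6.a (Seven) counts from release and the synopsis from baseline.
- State whether records are still collected after an 11.b withdrawal, where the signed authorization allows it.

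The cost is protocol and SAP wording, a dated rather than summed extraction, and some added analysis; no new visits or participants. The result will rest on data being missing at random given the records, which the sensitivity analysis probes. It cannot help people whose records also stop.

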7. RISKS AND BENEFITS

7. a. Risks

The risks associated with this study are minimal and no greater than those experienced in the course of everyday life. They include breach of confidentiality and the possibility that study participants could become emotionally upset by interview questions. The potential risks are minimal, no more than encountered in everyday life with the potential benefits outweighing the risks.

7.b. Benefits

This research is highly relevant for mental health and criminal justice authorities at local, state and national levels and has the potential to have a broad impact on criminal justice policy and practice. Findings from this research promise to support the development of an intervention that can improve outcomes for people with mental illness in prisons. This study addresses one of the most pressing public health and public safety issues facing our country today. The knowledge to be gained in the study will enable the research team- and other investigators- to undertake larger-scale, RCTs to establish the effectiveness of T4C-MI. Additionally it is possible that participants assigned to receive T4C-MI could receive additional support from this intervention and could realize fewer behavioral infractions and time in administrative segregation while incarcerated.

8. DATA COLLECTION AND MANAGEMENT

8.a. Data Collection

The study PI will facilitate an orientation for all research staff on how to conduct research interviews. The PI will also facilitate a brief training on the use of the study measures when necessary. All research staff involved in interviewing participants will have a minimum of a graduate degree in social work or a related discipline. Research staff will be trained to look for signs of distress, stop interviews when necessary, and connect participant with mental health services when required.

9. STATISTICAL ANALYSIS

Given the preliminary nature of this study, statistical analyses of our outcomes will not be conclusive; rather we will examine the data for trends across time rather than relying exclusively on tests of statistical significance.

9.a. Primary Outcomes

The primary outcomes of this study are: Aggression, Receipt of Behavioral Infractions, and Time Spent in Administrative Segregation (see Appendix B).

9.b. Secondary Outcomes

The secondary outcomes of this study are those measures listed as Treatment Targets in the conceptual model: Interpersonal Problem Solving, Criminal Attitudes and Associates, and Levels of Impulsivity (see Appendix B).

9.c. Statistical Methods

Treatment Targets and Study Outcomes that are collected via a standardized measure (i.e. Social Problem Solving, Criminal Attitudes and Associates, Impulsivity, and Aggression) are collected at baseline as well as during follow-up periods (see Appendix A). Study Outcomes that are collected via administrative data (i.e. receipt of behavioral infractions and time spent in administrative segregation), however, are not collected as baseline, rather are summed cumulatively over the period extending from the 3-month follow-up period through the 9-month follow-up period.

To examine the impact of T4C-MI on study outcomes that are measured dichotomously and only collected during follow-up periods (i.e. receipt of disciplinary fractions and administrative segregation), we will use chi-square tests to examine between-group differences during the post-test period. To examine between-group post-test differences when these outcomes are measured as counts (i.e. number of behavioral infractions received and days spend in administrative segregation), nonparametric tests will be used to test differences in group medians (e.g. Mann-Whitney Test) and regressions that can accommodate count data (e.g. Poisson, negative binomial) will be employed.

For Treatment Targets and Study Outcomes that are measured continuously and collected at both baseline and follow-up periods (i.e. Social problem solving, impulsivity, criminal attitudes and associates, and aggression), we will use T-tests to examine between-group differences at posttest as well as mixed effects linear models where measurement occasion at level 1 is nested within the individual at level 2.

The potential mediation effects of the proposed primary treatment targets on study outcomes will be explored using structural equation modelling (SEM) and generalized structural equation modelling (GSEM) frameworks to accommodate for variables that are measured both continuously and dichotomously.

9.d. Sample Size and Power

The sample will include up to 112 participants. Given the preliminary nature of this pilot study, our goals are not to fully test our hypotheses nor estimate effect sizes associated with T4C-MI. The main purpose of this R34 is to collect data on available sample size, sample attrition and sample retention and the generation of data and information necessary to conduct comprehensive power calculations for an R01. Nevertheless, here, the likelihood of detecting statistical significance will be increased due to the use of a longitudinal design with up to four measurements per subject on our treatment targets and outcome

measures. Also, our longitudinal design allows for each participant to serve as his/her own historic control, eliminating between-subjects variation and reducing standard errors, which increases power.

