Study Phases	
(1) Study Recruitment and Informed Consent
 
A) Prison Staff will provide study personnel with list of potentially eligible participants.B) Study staff will invite potentially eligible participants to meet with them to discuss study. Study staff will complete informed consent with all potential participants who agree. 
(2) Study Screening- All potential participants who agree to participate in the study after informed consent is completed will participate in a screening interview to determine study eligibility.
 
(3) All participants who are found eligible at the end of the screening interviews will be randomized to one of the two study arms (e.g. experimental or control condition). These individuals will make up the study sample
 
(4) Baseline interviews will be completed with all study participants.
 
(5) Study participants who are randomized into the experimental condition will participate in the study intervention. Those who are randomized into the control condition will receive standard prison treatment and programming.
 
(6) Follow up: Study participants will participate in follow-up interviews at 3- and 6- months post-baseline.
 
(7) Administrative data related to behavioral infractions and administrative segregation will be gathered at 9-months post-baseline.

Screening	
Study Treatment	
Follow-Up	

The statistical analyses of this study will explore the treatment effect of the study intervention on the study outcomes (aggression, receipt of behavioral infractions, and time spent in administrative segregation) and the study treatment targets (impulsivity, social problem solving, and criminal attitudes and associates). Additionally, mediation analyses will be conducted to explore whether treatment effects on study outcomes operate indirectly through study treatment targets.

DATA AND SAFETY MONITORING PLAN	This is a small-scale, pilot study with a relatively small number of subjects; thus, in lieu of a Data and Safety Monitoring Board, the PI will perform the monitoring function as part of the general oversight and scientific leadership of the study
---------------------------------	---

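### The trend, own-control and four-measurement statements do not hold for behavioral infractions and administrative segregation, which have one 3-9-month total per person and no baseline

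*Combined protocol and SAP*

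**What the plan says.** Section 9 opens by calling the analyses not conclusive and states that "we will examine the data for trends across time rather than relying exclusively on tests of statistical significance". Section 9.a names the primary outcomes: "The primary outcomes of this study are: Aggression, Receipt of Behavioral Infractions, and Time Spent in Administrative Segregation".

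Section 9.c treats the three differently. Aggression is an interview measure taken at baseline and at follow-up, and is to be analyzed by t-tests and a mixed linear model with occasion nested in person. The two outcomes from prison records "are not collected as baseline, rather are summed cumulatively over the period extending from the 3-month follow-up period through the 9-month follow-up period". The synopsis (Study Phases) describes a single collection: "Administrative data related to behavioral infractions and administrative segregation will be gathered at 9-months post-baseline". Appendix A marks both outcomes only in the nine-month column.

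For the dichotomous form of these two, "we will use chi-square tests to examine between-group differences during the post-test period". For the count form, "nonparametric tests will be used to test differences in group medians (e.g. Mann-Whitney Test) and regressions that can accommodate count data" are planned. No time term and no baseline covariate is named.

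Section 9.d then argues that power is helped by "up to four measurements per subject on our treatment targets and outcome" measures, and by each participant acting as his or her own earlier control. Section 6.a (step six) says that the baseline interview covers the study outcomes, without excepting the two taken from records.

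**The concern.** A single total per person has no course over time and nothing earlier to compare it with. Section 9 and Section 9.d are written as if they covered all outcomes, yet they cannot apply to the two that come from prison records. Those two, with aggression, are what the intervention is meant to change.

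Two things are at stake. First, the power argument in Section 9.d credits these outcomes with repeated measurement and within-person control that they do not have. Second, Section 9.d says that the pilot exists largely to supply inputs for the power calculations of a later trial. For count outcomes those inputs include rates by interval and the correlation between earlier and later counts, and the plan as written produces neither.

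**Working it through.** **1. Occasions per subject, counted from the marks in Appendix A**

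| Measure | Role | Occasions | Number |
|---|---|---|---|
| Aggression | primary | baseline, 3, 6 months | 3 |
| Behavioral infractions | primary | 9-month records check | 1 |
| Administrative segregation | primary | 9-month records check | 1 |
| Social problem solving | secondary | baseline, 3 months | 2 |
| Criminal attitudes and associates | secondary | baseline, 3 months | 2 |
| Impulsivity | secondary | baseline, 3 months | 2 |

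The plan's figure of up to four is not reproduced; the maximum is 3. Section 6 does count up to four interviews, but the first is screening, where no outcome is measured. Baseline, 3, 6 and 9 months also make four time points, but no single measure is taken at all of them.

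**2. What the total covers.** Read as months 3 to 9, it uses 6 of 9 post-baseline months (6/9 = 67%) and omits 3 (3/9 = 33%). The intervention lasts 12-14 weeks, which is 84/30.44 = 2.8 to 98/30.44 = 3.2 months. The omitted part is therefore roughly the delivery period, and a 14-week course runs slightly past month 3 even if it starts on the day of baseline. The wording could also be read as including the first three months. On that reading nothing after baseline is omitted, but there is still one total and no baseline.

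**3. Statements against outcomes**

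- Trend across time: not possible with 1 value; a change with 2; a short course with 3.
- Own control: needs an earlier value. Aggression and the targets have one; the two record-based outcomes do not.
- Section 6.a, step six, conflicts with Section 9.c and Appendix A on whether these two have a baseline. The latter are the more specific.

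**4. What an earlier count might add (illustration only).** The documents give no alpha, power, effect size or correlation, so these are assumptions: two-sided 0.05, 80% power, 112 people split equally (56 per arm), no attrition, and a linear model on a transformed count.

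- Detectable standardized difference with the single total: (1.960 + 0.842) × √(2/56) = 0.53.
- Adjusting for an earlier count with correlation r multiplies residual variance by 1 − r², and the detectable difference by √(1 − r²).

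| Assumed r | 1 − r² | Cut in variance | Detectable difference |
|---|---|---|---|
| 0.3 | 0.91 | 9% | 0.51 |
| 0.5 | 0.75 | 25% | 0.46 |
| 0.6 | 0.64 | 36% | 0.42 |

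**The case against.** The strongest defense is that one general introductory sentence does not fit two outcomes, and little follows from that. Much of this stands.

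- A reader might infer that the plan has no usable analysis for these outcomes. It does. Section 9 says only that it will not rely exclusively on significance tests, and chi-square, Mann-Whitney and count regression on a post-treatment total are all workable.
- A reader might infer that no trend can be examined anywhere. Aggression has three occasions and a mixed model, and each target has two occasions.
- A reader might infer that leaving out months 0-3 is an error. Section 9.c treats these as post-test outcomes, and starting the count at about the end of a 12-14-week intervention is defensible.
- A reader might convert the variance reduction into extra participants, for example 112/0.75 = 149 at r = 0.5. The documents do not support that. The correlation is assumed, the formula is for a linear model, chi-square and Mann-Whitney take no covariate, and in count models the Poisson variation remains after adjustment. In addition, 112 is a ceiling, and Section 11.b withdraws people who are transferred or released.
- A look-back may not be available for everyone. Eligibility requires a year left to serve but no minimum time already served, and Section 6.b says only that the authorization covers administrative data on the study outcomes.

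The pilot status does not remove the point. Because Section 9.d gives the study the task of informing a later power calculation, interval rates and the correlation between earlier and later counts are worth having.

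**Conclusion.** For two of the three primary outcomes, the trend statement in Section 9 and the own-control and four-measurement statements in Section 9.d cannot hold as the outcomes are defined. For aggression and the treatment targets they hold in part, and four occasions is wrong for every measure. This rests on a direct count from Appendix A and on Section 9.c, and it does not depend on how the start of the window is read.

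The planned comparisons are not invalidated. What is lost is some precision and some information for the later trial. The size of the precision loss is unknown: 9-36% of residual variance for an assumed correlation of 0.3-0.6, on a linear approximation without attrition, and probably less for sparse counts. The change is advisable because it is cheap, not because the trial would otherwise fail.

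**What to change.** 1. Keep months 3-9 as the primary window, and state plainly whether it starts at month 3.
2. In the same nine-month records pull, extract dated infractions and segregation days for months 0-3, 3-6 and 6-9, with days in custody in each period as exposure. The documents do not say that the records carry dates, but a person-specific 3-9-month total implies it.
3. Where the records exist and the authorization covers them, extract the same for a fixed look-back that ends before randomization. It should end there because, under Section 6.a, participants learn their arm before the baseline interview.
4. Adjust the planned count regression for the pre-randomization rate. Report rates by arm and interval, and the 0-9-month total, as supportive. A repeated-measures count model is optional, since events may be sparse.
5. If the look-back cannot be obtained, limit the own-control statement to the interview measures. If the interval counts are not extracted, limit the trend statement likewise.
6. In either case correct the figure of up to four in Section 9.d, and reconcile Section 6.a (step six) with Section 9.c and Appendix A.

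The cost is a somewhat larger extract, some cleaning, and a check of the authorization's scope; there is no added participant contact. Recently admitted participants will have short prior exposure, so their earlier rates will be imprecise or missing, and the plan should say how these are handled.
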